## **Insulin therapy and concurrent treatments**

Concurrent treatments will be recorded at enrolment and their variations (if any) during the study will be collected. Patients will be asked to maintain the same formulations of insulin used at enrolment, with dose adjustments whenever needed for maintaining an adequate glycemic control.

## **Statistical plan**

### **Determination of sample size.**

The sample will be composed of 27 patients. This will allow to reach a 80% power of detecting ( $p < 0.05$ ) a difference in HbA1c between groups > 0.5%, assuming a standard deviation of 0.83%.

Principal analysis (superiority): Variations of HbA1c in the two study phases will be compared using Student's paired t tests, which will also be used to compare end-of-treatment and baseline HbA1c for each treatment phase. A repeated measure linear regression model will be applied to compare the effects of the two treatments adjusting for treatment sequence. These analyses will be performed both by intention to treat (primary analysis), i.e. including all randomized patients and imputing missing data (if any) with the last observation carried forward (LOCF) method, and by protocol, i.e. restricted to patients actually using planned treatments.

Secondary endpoints: the same methods will be applied for analyses of secondary endpoints.

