## Study endpoints

The **primary endpoint** is the superiority of SAP versus MDI on HbA1c.

**Secondary endpoints** include:

- 1) Severe hypoglycemia
- 2) Change in body weight
- 3) Local reactions on the site of insulin administration and/or monitoring of glucose
- 4) Treatment satisfaction, measured using the Italian validated version of the WHO Diabetes Treatment Satisfaction Questionnaire.
- 5) Patients' preference for either treatment

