## Study design

The study is designed as a single-center, open-label, cross-over randomized trial.

Lo studio è disegnato come un trial randomizzato in cross-over, in aperto.

After verification of inclusion and exclusion criteria, enrolled patients will be randomized (using a computer-generated random number sequence) 1:1 to either SAP or MDI for 4 months, and then switched to the alternative treatment.

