## Duration of the study

- *Duration of enrolment:* 18 months
- *Duration of treatment:* 4 months for each treatment phase, with no wash-out.

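### The reference point for each HbA1c variation is undefined; if it is the start of each phase, the crossover contrast estimates about 1.5 times the SAP-MDI difference

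*Combined protocol and SAP*

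**What the plan says.** The primary endpoint (Study endpoints) is "the superiority of SAP versus MDI on HbA1c", with no time point and no reference to change. The principal analysis (Statistical plan) reads "Variations of HbA1c in the two study phases will be compared using Student's paired t tests", and the same sentence adds that paired tests will also "compare end-of-treatment and baseline HbA1c for each treatment phase". It continues: "A repeated measure linear regression model will be applied to compare the effects of the two treatments adjusting for treatment sequence". The outcome of that model is not stated. Missing values are handled by "imputing missing data (if any) with the last observation carried forward (LOCF) method".

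The sample size is built on "a difference in HbA1c between groups > 0.5" (per cent HbA1c) with an SD of 0.83%. The plan does not say what that SD describes.

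Patients are treated for one phase "and then switched to the alternative treatment" (Study design), and the phases last "4 months for each treatment phase, with no wash-out" (Duration of the study). Secondary endpoints, including body weight change, are to be analysed in the same way as HbA1c.

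**The concern.** A statistician could follow this text literally and run either of two analyses. In one, both variations are measured from enrolment. In the other, each is measured from the start of its own phase, which the phrase about a baseline for each phase suggests. In a crossover without wash-out these are different quantities. The second baseline is already a treated value, so subtracting it brings part of the first treatment's effect into the change credited to the second.

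At stake are the reported size of the HbA1c benefit, its confidence interval, the power of the primary test and the meaning of the before/after tests. In an open-label trial it also matters that this choice is not left until results are known.

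**Working it through.** **Inputs.** From the documents: 27 patients, 1:1 allocation, two 4-month phases, no wash-out, target difference 0.5%, SD 0.83%. Assumptions: 0.83% is the SD of the within-patient end-of-phase difference, and tests are two-sided at 5%. Y0, Y1 and Y2 are HbA1c at enrolment, month 4 and month 8. The mean shifts from enrolment are s on SAP and m on MDI. The range tried is m from -0.5 to +0.25 with s - m = -0.5.

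**The plan's own figure.** The normal approximation gives (1.960 + 0.842)² × 0.83² / 0.5² = 21.6, so 22 patients. The paired t test needs 24 (power 80.7%), and 27 patients give 85.4%. So 27 is not reproduced exactly but errs on the safe side. The target difference in this calculation is s - m.

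**Expected contrast, SAP minus MDI.**
- Both variations from enrolment: Y0 cancels within patient, and both sequences give s - m. Factor 1.
- Phase start, SAP first: (Y1 - Y0) - (Y2 - Y1), mean s - (m - s) = 2s - m.
- Phase start, MDI first: (Y2 - Y1) - (Y1 - Y0), mean (s - m) - m = s - 2m.
- Balanced average: 1.5(s - m). A true -0.50 becomes -0.75.

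**Unequal sequences.** With k SAP-first patients, the phase-start contrast is (s - m) + [k·s - (27 - k)·m]/27.

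| k | m = -0.5 | m = 0 | m = 0.25 |
|---|---|---|---|
| 13 | -0.722 | -0.741 | -0.750 |
| 14 | -0.778 | -0.759 | -0.750 |
| 10 | -0.556 | -0.685 | -0.750 |
| 17 | -0.944 | -0.815 | -0.750 |

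The plan states no blocking. Under simple randomisation a 13/14 or 14/13 split occurs in about 30% of trials, and one as uneven as 10/17 or worse in about 25%.

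**Missing data and carry-over.** The bracketed term uses only Y0 and Y1, so events in phase 2 leave it unchanged.
- LOCF for 3 of 27 month-8 values: end-of-phase 0.5 × 24/27 = 0.44, phase-start 0.67-0.72.
- Symmetric carry-over of a fraction c: factor 1.5 - c for phase-start, 1 - c for end-of-phase. At c = 0.10 and balance: 0.70 against 0.45.

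**Precision, by simulation at a 13/14 or 14/13 split.** With equally correlated visits, the error SD of the phase-start contrast is √3 × 0.83 = 1.44, a 1.73-fold rise against a 1.5-fold rise in effect. With AR(1) correlation ρ between successive visits, the multiplier is √(3 - ρ).

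| | Phase-start | End-of-phase |
|---|---|---|
| Power, equal correlation | 61-75% | about 85% |
| Power, AR(1), ρ 0.3-0.85 | 65-87% | about 85% |
| 95% CI coverage of the true 0.50% | 82-92% | about 95% |

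**Type I error.** The phase-start test rejects in 3.4-5.5% of null trials near balance. With s = m = -0.5 and k = 17, the contrast has mean (-0.5 × 17 + 0.5 × 10)/27 = -0.13, and rejection is about 6%. Averaged over simple randomisation it is about 5%.

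**Before/after on MDI.** MDI-first patients give m and SAP-first patients m - s, so the balanced mean is m - s/2. With s = -0.5 and m = 0 this is a rise of 0.25, although MDI left HbA1c at its enrolment level. At a 13/14 or 14/13 split the test declares a rise in 27-32% of trials.

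**Regression.** Fitted to phase-start changes with treatment and sequence terms, the treatment coefficient equals the paired mean, so it carries the same factor. Fitted to end-of-phase HbA1c, the factor is 1.

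**The case against.** The strongest reply is that the harm belongs to one reading only. The endpoint and the sample size both speak of HbA1c, not of change, and the phrase about a baseline can mean one enrolment value compared with the end of each phase. That stands: the documents establish an undefined term. A reader might infer that the planned primary analysis is biased by half, but the text does not go that far.

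A reader might also infer that the inflated estimate makes superiority easier to claim. The calculations do not support this in general. Near balance type I error is about nominal, and power is lower under equal correlation. Only with strong serial correlation does it reach that of the end-of-phase test.

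Nor is the exaggeration unconditional. At c = 0.25 the two contrasts are equally far from the truth (factors 1.25 and 0.75), and beyond that the phase-start contrast is nearer. With m = 0, coverage of the true 0.50% at c = 0.25 is about 93% for phase-start and 88% for end-of-phase. The documents give no carry-over figure. This does not argue for the phase-start contrast, whose excess merely offsets an unrelated bias by chance.

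The apparent rise on MDI is one case. With s = m - 0.5 the balanced MDI change is m/2 + 0.25, which is zero at m = -0.5. The Study aim calls MDI optimized, so m = 0 is not implied. The change is still 0.25 away from m at m = 0, and 0.50 away at m = -0.5.

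**Conclusion.** The point holds as a conditional one, and it should be fixed because it concerns the primary contrast. The reference for the variations is not defined. Measured from enrolment, the analysis is sound. Measured from the start of each phase, it does not estimate the 0.5% difference on which the trial was sized, but about 1.5 times that.

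The factor 1.5 rests on balanced sequences, complete data and no carry-over. The power and coverage figures rest also on the assumed meaning of the 0.83% and on the correlation between visits. The main harm is to the estimate, its interval and the before/after tests, with a likely loss of power. Type I error is a minor matter, reaching about 6% only when the split is as uneven as 10/17 and both treatments lower HbA1c by 0.5%. Adjusting for sequence does not remove the factor if the model's outcome is change from phase start.

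**What to change.** State in the Statistical plan that the principal paired test and the repeated-measures model use HbA1c at the end of each 4-month phase, compared as SAP minus MDI within patient, without subtracting the phase-2 starting value. For the paired contrast this is the same as change from enrolment in both phases. State that any before/after comparison is measured from the enrolment HbA1c, and that body weight follows the same rule.

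The cost is one or two sentences. No visit, measurement or patient is added, because enrolment and end-of-phase values are already needed. The wording should be fixed before any outcome data are examined.

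### The principal HbA1c analysis of this two-period cross-over does not secure adjustment for period, and its unrestricted LOCF can score a patient on one treatment with a value from the other.

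*Combined protocol and SAP*

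**What the plan says.** Under Study design, patients are "randomized (using a computer-generated random number sequence) 1:1 to either SAP or MDI for 4 months, and then switched to the alternative treatment"; no blocking is mentioned. Duration of the study gives "4 months for each treatment phase, with no wash-out". An HbA1c taken at the switch is therefore an on-treatment value from phase 1.

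The analysis is described under Statistical plan, in the paragraph on the principal analysis:

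- **Test.** "Variations of HbA1c in the two study phases will be compared using Student's paired t tests". The same test is to "compare end-of-treatment and baseline HbA1c for each treatment phase". What baseline means for phase 2 is not stated.
- **Model.** "A repeated measure linear regression model will be applied to compare the effects of the two treatments adjusting for treatment sequence". No formula is given, and period is not named.
- **Missing data.** The primary intention-to-treat analysis covers all randomized patients, "imputing missing data (if any) with the last observation carried forward (LOCF) method". Whether a value may cross from one phase to the other is not stated.
- **Second population.** A per-protocol analysis is "restricted to patients actually using planned treatments".

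The sample-size statement uses 27 patients, a difference of 0.5 and 80% power, "assuming a standard deviation of 0.83" (in % HbA1c). It does not say whether this is the SD of a paired difference or of a single measurement. The secondary endpoints take the same methods.

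**The concern.** In a two-period cross-over each patient's treatment difference contains any general change between months 1-4 and months 5-8. That change enters with opposite signs in the two sequences. A paired t test pools the sequences, so the shift adds to the variance and, if the sequences are unequal in size, biases the estimate. A sequence main effect is a between-patient term. With complete data it leaves the within-patient treatment estimate and its standard error unchanged.

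A patient with no phase-2 HbA1c has nothing from that phase to carry forward. Unrestricted LOCF then reaches back to the other treatment, and the patient contributes a zero difference whatever the true effect.

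At stake are the size of the reported treatment effect and some power. A smaller definitional question about the phase-2 baseline belongs with these.

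**Working it through.** **Inputs.** From the Statistical plan: N = 27, difference 0.5, SD 0.83, two-sided 5% (sidedness assumed). Assumptions not in the documents: 0.83 is the SD of the paired difference, excluding any period shift; period shift π of 0.3 or 0.5; 1 to 5 patients without a phase-2 value; simple (unblocked) randomization where splits are averaged.

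**The plan's own figure.** A two-sided paired t test with 0.5/0.83 has 80.7% power at N = 24 and 85.4% at N = 27. The stated 27 is therefore more than 80% power needs on this reading. It matches 24/0.9 = 26.7, rounded up, but no dropout allowance is stated. The baseline for comparison below is 85%.

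**Period effect.** The patient-level difference has mean τ + π in one sequence and τ − π in the other.

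- Bias of the paired estimate = π(n₁ − n₂)/27. At 13/14 this is π/27, or 0.011 and 0.019 in absolute value. At 9/18 it is π/3, or 0.10 and 0.17.
- Effective SD at 13/14 is about √(0.83² + π²·27/26): 0.88 for π = 0.3 and 0.97 for π = 0.5.
- Adjusted SE = ½·0.83·√(1/n₁ + 1/n₂): 0.160 at 13/14 (the paired test with no shift has 0.83/√27 = 0.160) and 0.169 at 9/18.

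Simulation with these inputs (power averaged over the two directions of the shift):

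| Situation | π = 0 | π = 0.3 | π = 0.5 |
|---|---|---|---|
| 13/14, paired power | 85% | 82% | 76% |
| 13/14, adjusted power | 85% | 85% | 85% |
| 13/14, paired type I error | 5% | 3.8% | 2.4% |
| 12/12 (24 completers), paired power | 81% | 77% | 70% |
| 12/12, adjusted power | 80.5% | 80.5% | 80.5% |
| 9/18, paired type I error | 5% | about 7.5% | about 10.7% |

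A split of 9/18 or worse has probability 2·P(X ≤ 9), X ~ Bin(27, ½), which is 0.122. Averaged over all splits, bias is zero and type I error is 5.0%; paired power is 85.4%, 80.8% and 73.1% for shifts of 0, 0.3 and 0.5, against 83.8% adjusted.

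**What sequence adjustment does.** One simulated data set with a 9/18 split and shift 0.5, estimate (SE):

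- paired, and treatment + sequence: 0.0656 (0.1778) for both
- treatment + period, and treatment × sequence: −0.1427 (0.1462) for both

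The planned model is thus period-adjusted if sequence enters through its interaction with treatment, or is fitted to within-patient differences. It is not if sequence enters only as a main effect.

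**LOCF.** With k of 27 patients scored as zero, the expected estimate is 0.50·(27 − k)/27.

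| k | Estimate | Coverage of 0.50 | Power, LOCF | Power, completers |
|---|---|---|---|---|
| 1 | 0.48 | 95% | 84% | 84% |
| 2 | 0.46 | 95% | 82% | 82% |
| 3 | 0.44 | 94% | 81% | 81% |
| 5 | 0.41 | 91% | 77% | 77% |

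The interval covers its own attenuated expectation 95-96% of the time, and type I error is 5%.

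**Phase-2 baseline.** Let B, S and M be the HbA1c at entry, at the end of the pump phase and at the end of the MDI phase. With B as the baseline for both phases, the contrast of changes is S − M. With the switch value as the phase-2 baseline:

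- pump first: (S − B) − (M − S) = 2S − M − B
- MDI first: (S − M) − (M − B) = S − 2M + B

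The mean at equal sequences is 1.5(S − M). If MDI leaves HbA1c at its entry level, a true 0.50 is estimated as 0.50·(27 + 13)/27 = 0.74 with 13 pump-first patients, or 0.50·(27 + 14)/27 = 0.76 with 14.

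**The case against.** The best defence is that the model may already do the job. Adjusting a cross-over for sequence can mean a treatment-by-sequence term, which is algebraically the same as period adjustment. That stands: a reader might infer that the plan has no period-adjusted analysis at all, and the wording does not support this. What remains is that the wording does not settle it, and that the paired test listed beside the model has no such adjustment on any reading.

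The period harm is also modest. Near-equal sequences make the paired test conservative, and the documents give no reason to expect a shift as large as the target effect. If 0.83 already contains the shift, planned power is met: 87% and 90% for the paired test at shifts of 0.3 and 0.5. A reader might infer that the trial's type I error is inflated; this is so only conditionally on an uneven split together with a sizeable shift.

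On LOCF, the plan does not prescribe carrying across phases; it merely does not rule it out. The problem arises only for a patient with no phase-2 HbA1c, and the text available does not show how often HbA1c is measured. The per-protocol analysis would probably exclude most such patients. Attenuation is conservative for a superiority claim. A reader might take the lower coverage to mean that the interval is too narrow, but it covers its own expectation properly. The fault is bias toward zero, not understated variance.

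The baseline point is conditional. With the entry value there is no problem, and with the switch value type I error stays nominal. Nor may its effect be added to the LOCF result, because the LOCF figures assume end-of-phase values or a common baseline.

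**Conclusion.** The point holds as a case for a cheap improvement. It does not show the trial to be invalid. Two things are established from the text: one of the two principal analyses cannot adjust for period while the other may or may not, and LOCF has no phase limit.

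For shifts of 0.3 to 0.5, the paired test loses about 3 to 9 points of power at 13/14 (85% to 82% and 76%). At 9/18 it has bias of 0.10 to 0.17. Carrying phase-1 values takes a true 0.50 to 0.44 with 3 lost and to 0.41 with 5 lost. The shifts, the numbers lost and the reading of 0.83 are all assumptions. No overall false-positive inflation is shown, and LOCF costs no power compared with completers.

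The undefined phase-2 baseline is a secondary matter for clarification: the same data could be reported as about 0.50 or about 0.75.

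**What to change.** Name one primary analysis: a linear mixed model on observed end-of-phase HbA1c with fixed effects for treatment and period (sequence may stay), a random patient effect and small-sample degrees of freedom. Fit it by likelihood to all randomized patients with at least one end-of-phase value, and carry no value between phases. If change is reported, measure it from the single study-entry value. Keep the paired t test, and LOCF in all randomized patients, as sensitivity analyses.

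In simulation with 3 or 5 lost, within-patient correlation 0.3 or 0.6 and shift 0 or 0.3, this model estimated 0.496 to 0.505 for a true 0.50. Coverage was 94.1-95.2% and type I error 4.8-5.1%. Power was 81-83% with 3 lost and 78-80% with 5.

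Costs:

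- One degree of freedom and revised wording; no new data.
- If there is no period shift, about 0.2 points of power at 13/14, 1.6 averaged over splits (85.4% to 83.8%) and 4 at 9/18. Under simple randomization, adjustment gains power only from a shift of about 0.2 upward.
- A missing-at-random assumption, which is open to question in an open-label trial.
- Patients with no end-of-phase value leave the primary model; the LOCF sensitivity analysis still includes them.

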## Study aim

The trial is aimed at verifying the superiority of a sensor-augmented pump (SAP) system, in comparison with optimized multiple daily injections (MDI) of insulin, using degludec as basal insulin, with respect to glycemic control, incidence of severe hypoglycemia, body weight, local reactions, treatment satisfaction, and patient preferences.

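### Patient preference, a single choice per patient, is assigned HbA1c methods that mostly do not fit it, and LOCF does not suit the two event endpoints

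*Combined protocol and SAP*

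**What the plan says.** The Study aim extends the superiority question beyond HbA1c to "incidence of severe hypoglycemia, body weight, local reactions, treatment satisfaction, and patient preferences". Study endpoints lists five secondary endpoints. Two matter most here: patients' "preference for either treatment" and "Local reactions on the site of insulin administration and/or monitoring of glucose". Neither has a scale or time point.

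The Statistical plan describes the HbA1c analysis in four parts:

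- "Variations of HbA1c in the two study phases will be compared using Student's paired t tests"
- the same test, "which will also be used to compare end-of-treatment and baseline HbA1c for each treatment phase"
- a repeated measures regression to "compare the effects of the two treatments adjusting for treatment sequence"
- an intention-to-treat rule, "including all randomized patients and imputing missing data (if any) with the last observation carried forward (LOCF) method"

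It then disposes of all the secondary endpoints in one sentence: "the same methods will be applied for analyses of secondary endpoints". No section makes an exception for any endpoint.

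**The concern.** The HbA1c methods assume a value for each patient in each phase, a baseline, and a status at a visit that can stand in for a later one. Body weight and the satisfaction score have that structure. Preference, as worded, does not. Severe hypoglycemia and local reactions build up over four months and are not a status at a visit.

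If the sentence stands, the test for preference, its denominator and the treatment of patients who make no choice must all be settled later. The Study design section makes this an open-label trial, so they could be settled with the data in view. The event endpoints leave a similar but smaller choice of scale, plus an imputation rule that misstates what was observed.

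**Working it through.** **Inputs.** 27 patients and p<0.05 come from the Statistical plan; I take tests as two-sided, which the plan does not state. Two four-month phases come from Duration of the study. The plan gives no event rate, preference share or power for any secondary endpoint, so there is no stated figure to reproduce. The 27 was set for HbA1c and is used here only as the number of patients. Preference splits and event frequencies below are assumptions.

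**1. Fit of each assigned method to a single choice.**

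| Assigned method | Needs | Does preference supply it? |
|---|---|---|
| Paired t test on phase variations | a value per phase | Only if the choice is recoded as a contrast, which is not stated |
| End of phase v baseline | a baseline | No |
| Repeated measures regression | repeated values | No |
| LOCF over all randomized | an earlier observation | No; a patient who never starts phase 2 has nothing to carry forward |

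**2. Does the unstated coding matter?** Take 19 v 8 among 27.

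- Coded +1/-1: mean = (19 - 8)/27 = 0.407; SD = 0.931; t = 0.407/(0.931/√27) = 2.27 on 26 df; p=0.031.
- Exact binomial: p = 2 × P(X ≥ 19 | 27, 0.5) = 0.052.

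The two analyses fall on opposite sides of 0.05. If all 27 choose, the coded t test has a type I error of 5.2%. The exact test rejects from 20 of 27 (p=0.019; 95% CI 54% to 89%), so its type I error is 1.9%.

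**3. Does the denominator matter on fixed data?** Take 17 v 5, with 5 stating no choice.

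- Choosers only: 2 × P(X ≥ 17 | 22, 0.5) = 0.017.
- The five counted against: 2 × P(X ≥ 17 | 27, 0.5) = 0.25.

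**4. Is the paired t test invalid for yes/no events?** Code each patient's difference as +1, -1 or 0. Let the number of discordant patients be m ~ Binomial(27, share), split Binomial(m, 0.5) under no treatment or period effect. Sum the probability of every outcome with p<0.05, counting m = 0 as no rejection.

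| Discordant share (assumed) | Type I error |
|---|---|
| 5% | 0.5% |
| 10% | 2.6% |
| 20% | 4.9% |
| 50% | 4.5% |

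The maximum over 5% to 50% is 4.9%, so the test does not inflate false positives.

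**5. Does the event scale matter?** Six patients with an event in one phase and none in the other gives p=0.011 as yes/no. On counts, with five patients having one event and the sixth having 2, 3, 4 or 5, p = 0.017, 0.030, 0.047 and 0.067. Significance is lost only when one patient has five events.

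**6. LOCF on accrued events.** There are two literal readings.

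- A patient leaves during a phase and the partial count stands for the whole phase. With 2 of 4 months observed (assumed), a count c is read as c/4 per month when it was c/2, so the rate is halved.
- A patient leaves after phase 1 with y events, and LOCF enters y for the other treatment. The difference is y - y = 0 whatever the treatments do.

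**The case against.** The protocol gives no instrument or time point for preference. If it were rated separately after each phase, the assigned methods could be used. That is possible, but no such rating is described; only satisfaction has a named questionnaire, and the wording describes a choice between treatments. The objection strengthens the case for a definition.

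A reader might infer that preference cannot be analysed by a t test at all. The documents do not support that: a coded contrast is computable and its type I error is close to 5% if all 27 choose. What stands is that the coding is not in the plan and that the choice of test can change the conclusion.

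A reader might also infer that the t test is wrong for the event endpoints and should give way to an exact paired test. Step 4 shows that it is not invalid. The exact Mainland-Gart test would be costly here: with 20% discordant and 90% of those favouring one treatment (assumed), its power is about 14% against 50% for the paired t test. Replacing the test is a trade-off and not a correction.

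Finally, LOCF matters only if data are missing, and the scale example needs one patient with many events. Both are fair limits on the size of the event part.

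**Conclusion.** The point holds for preference: three of the four assigned elements do not fit a single choice, and the fourth needs a coding that the plan does not give. On fixed data the p-value moves from 0.031 to 0.052 with the test and from 0.017 to 0.25 with the denominator. This rests on reading the endpoint as one choice per patient, as Study endpoints words it, and on assumed splits.

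For severe hypoglycemia and local reactions the point is narrower. The scale should be fixed and LOCF replaced; the paired t test may stay. Body weight and the satisfaction score are not affected. It would be wrong to infer that the HbA1c result is weakened: only secondary endpoints are involved. The change should be made, but the trial's main conclusion does not depend on it.

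**What to change.** In the secondary endpoints sentence of the Statistical plan:

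- **Preference.** Exempt it from the HbA1c methods. State that it is one choice recorded after both phases and tested by exact binomial against 50% among patients who state a preference, with an exact 95% CI. To handle order, add a sequence-stratified Fisher test: sequence against whether the preferred treatment was the one taken first. Report the number with no preference or no second phase. Use no LOCF.
- **Severe hypoglycemia and local reactions.** Fix the scale beforehand, as patients with at least one event per phase or as events per exposure time. Use observed events and exposure time in place of LOCF. The paired t test may stay; Mainland-Gart should not be the default.
- **Body weight and satisfaction score.** Keep the planned methods.

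The cost is wording only. If all 27 choose, power of the binomial test is 84% when 80% truly prefer one treatment and 41% when 70% do. With 14 and 13 patients per sequence, the Fisher test has 86% and 45%. If only 22 choose (assumed), the binomial figures fall to 73% and 31%. A yes/no event scale sets aside repeat events; a rate keeps them but may be unstable when events are few.
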